## 10.2. Clinical Laboratory Tests

The tests outlined in [Table 8](#) will be performed at the specified time points described in the Schedule of Activities.

**Table 8: Clinical and Safety Related Laboratory Tests Performed at Site**

Hematology	CMP/Metabolic	Urine
WBC count	Ca ++	β-hCG a
RBC count	Random Glucose	Drug screen b
Hemoglobin	Albumin	
Hematocrit	Na +	
Platelet count	K +	
MPV	Total Protein	
RDW	Bicarbonate	
MCV	Chloride	
MCH	BUN	
MCHC	Creatinine	
(no differential)	Alkaline Phosphatase	
	AST/SGOT	
	ALT/SGPT	
	Bilirubin	

Hormones	Immunogenicity	Laboratory
Growth	Anti-glucagon-antibody	HbA1c
Cortisol		C-peptide
Epinephrine		HIVab
Norepinephrine		HCVab
Glucagon		HBsAg

a Female participants of childbearing potential require a negative pregnancy test at Screening. Pregnancy testing will be repeated at the last treatment visit.

b Drug screening performed at Screening and the 2 Treatment Visits will include: cocaine, THC, opiates, benzodiazepines, and amphetamines. Except as noted below, inclusion in the study requires all tests to be negative at screening with the exception of THC, which will be noted, but will not be considered exclusionary.

A central laboratory will be utilized for analysis of all variables with the exception of urine tests, and rapid PG measurements made during treatment visits. A procedures manual will be provided to each site by the central laboratory. This manual will cover procedures for the collection, processing and shipping of blood samples, along with the Clinical Laboratory Improvement Act (CLIA) certification and normal ranges for the central laboratory.

The central laboratory will provide sites with all supplies needed for collection, processing and shipping of all blood samples, including PK samples, as well as point-of-care urine pregnancy tests.

Rapid urine drug screen kits will be provided to the sites. If a subject tests positive for other than THC at screening, the subject will normally be excluded from further study participation. However, if subject reports use of a concomitant medication (prescription or OTC) that provides a reasonable explanation for a positive result other than THC, the subject may be allowed to participate in the study at the investigator's discretion. If the subject is not able to provide a reasonable explanation but still refutes a positive finding, a urine sample will be sent to the central laboratory for confirmation. The result of this confirmatory test will be considered definitive.

A central analytical lab will analyze the PK samples collected in this study. The procedures for preparing, storing and shipping PK samples to the analytical lab are discussed. To the extent possible based on storage limitations at the sites, PK samples will be batched so as to reduce the overall number of shipments. The main and back-up PK samples (i.e., Aliquots 1 and 2) for a particular subject should never be included in the same shipment.

During treatment visits, PG levels will be measured using a bedside rapid glucose analyzer (e.g. YSI 2300 or 2900). At each time point specified in Section 9.5, the results of both the black and white leads to one decimal place will be recorded in the source documents, with the average of the two values rounded up to the nearest one decimal place accepted as the PG level for the time point as per the following examples.

Example #1: black lead = 50.1 and white lead = 49.8

Calculation:  $50.1 + 49.8 = 99.9 / 2 = 49.95 = 50.0$  mg/dL recorded result

Example #2: black lead = 74.4 and white lead = 74.5

Calculation:  $74.4 + 74.5 = 148.9/2 = 74.45 = 74.5$  mg/dL recorded result

The glucose analyzer will be set to auto-calibrate following the standard practice at each site. Before each subject visit, performance checks will be made as per the standard practice at each site, and sites will maintain a log of these results.

### **10.3. Electrocardiogram (12-lead ECG)**

Single, supine 12-lead ECGs will be obtained at the pre-defined time-points outlined in Schedule of Activities as follows:

- 12-lead ECGs should be performed after the subject has rested quietly for at least 10 minutes in a supine position.
- 12-lead ECGs should be obtained before assessment of BP and heart rate, and prior to blood collections.

### **10.4. Blood Pressure and Heart Rate**

The BP and heart rate will be measured at the times specified in the Schedule of Activities. Additional or changes to collection times, or collection of BP and heart rate using automated devices is permitted, as necessary, to ensure appropriate subject's safety.

BP and heart rate will be measured in the sitting position with the subject's arm supported at the level of the heart, and recorded to the nearest mmHg. The dominant arm will be used throughout the study. The subject should be rested for at least 5 min. before the BP is obtained. SAFETY AND ADVERSE EVENT (AE) REPORTING

### **10.5. Definition of an Adverse Event**

An AE is any untoward medical occurrence in a clinical investigation subject administered a pharmaceutical product and which is not necessarily required to have a causal relationship with this treatment. An AE can therefore be any unfavorable and unintended sign, symptom, or disease temporally associated with the use of a medicinal product, whether or not considered related to the medicinal product. Examples of AEs include:

- Abnormal test findings.
- Clinically significant symptoms and signs.
- Changes in physical examination findings which are untoward and deemed clinically significant by the investigator.
- Allergy/hypersensitivity.

The criteria for determining whether an abnormal objective test finding may be reported as an AE are as follows:

- Test result is associated with accompanying symptoms,
- Test result requires additional diagnostic testing or medical/surgical intervention,
- Test result leads to a change in study dosing or discontinuation from the study, significant additional concomitant drug treatment or other treatment.

- Test result is considered to be an AE by the investigator or Sponsor.

Repeat of a test based on an abnormal result in the absence of the above conditions does not constitute an AE. Any abnormal test result determined to be an error does not require reporting as an AE.

A treatment-emergent AE (TEAE) is an AE that either commenced following initiation of study treatment or was present prior to study treatment but increased in frequency or severity following initiation of study treatment.

Standard medical terminology should be used in describing AEs. Informal descriptions should be avoided.

## **10.6. Reporting Adverse Events**

All observed or volunteered AEs regardless of treatment group or suspected causal relationship to the study treatment will be reported with two exceptions. Since it is being experimentally induced in this study, hypoglycemia will not be considered an AE in this study unless the event meets one of the definitions of an SAE (see Section 10.8). Injection site reactions will not be considered an AE unless a skin reaction or pain requires medical intervention.

For all AEs, the investigator must pursue and attempt to obtain information adequate to determine the outcome of the AE and to assess whether it meets the FDA criteria for classification as an SAE, requiring immediate notification to Xeris Pharmaceuticals. For AEs with a causal relationship to the investigational product, follow-up by the investigator is required until the event resolves or stabilizes at a level acceptable to the investigator to consider it closed, and Xeris Pharmaceuticals should concur with that assessment.

As part of ongoing safety reviews conducted by the Sponsor, the Sponsor may escalate any non-serious adverse event that is determined to be serious (according to the FDA definitions of an SAE). To assist in the determination of case seriousness, further information may be requested from the investigator to provide clarity and understanding of the event in the context of the clinical study.

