## **6. BACKGROUND AND RATIONALE**

### **6.1. Indication**

The proposed indication is for the prevention of severe hypoglycemia in diabetes mellitus patients with recurrent severe hypoglycemia.

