## **10.7. Reporting Period**

For all AEs, the reporting period to Xeris Pharmaceuticals begins from the subject providing informed consent, through the last subject Visit. All adverse events will be followed until resolution or the subject is medically stable.

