## 3.2 Secondary Objectives

### 3.2.1 Efficacy Objectives

1. Compare change in cumulative glucose infusion to maintain glucose at 50 mg/dL for the first 30 minutes after the 50 mg/dL is achieved.
2. Compare change in cumulative insulin infusion to maintain glucose at 50 mg/dL for the first 30 minutes after the 50 mg/dL is achieved.
3. Compare changes in the other counter-regulatory hormones: norepinephrine, glucagon, cortisol and growth hormone.
4. Compare changes from Induction 1 (baseline visit) to Induction 2 (visit 7, week 4) in subject responses to a validated hypoglycemia symptom questionnaire administered during induced hypoglycemia.
5. Compare changes from baseline to week 4 in CGM-derived hypoglycemia parameters of:
  - a. Proportional time spent with interstitial glucose < 70, <60 and <50 mg/dL.
  - b. Rate of hypoglycemic event episodes at plasma glucose < 70, <60, and <50 mg/dL.
  - c. Area over the curve (AOC) of the reduction from baseline in the interstitial glucose from T0 (defined as the date/time of the CSGI injection) to Tx, where x corresponds to time when interstitial glucose < 70, <60 and <50 mg/dL is achieved.
6. Compare change from baseline to week 4 in CGM-derived parameters of:
  - a. Average (mean) interstitial glucose and standard deviation
  - b. proportional time with  $70 \leq$  interstitial glucose < 180 mg/dL,
  - c. proportional time with interstitial glucose  $\geq$  180 mg/dL.
7. Describe subject reported hypoglycemic events
  - a. Symptomatic events confirmed with self-monitored glucose < 70 mg/dL.
  - b. Symptomatic events with no accompanying glucose meter reading or a reading  $\geq$ 70 mg/dL.
  - c. Asymptomatic events of self-monitored glucose < 70 mg/dL.
  - d. Severe hypoglycemia as defined by affected consciousness of hypoglycemic origin confirmed by a glucose meter reading <50 mg/dL, requiring external assistance, or prompt recovery upon hypoglycemia treatment.
8. Describe change from Induction 1 (baseline visit) to Induction 2 (visit 7, week 4) of unawareness measured by the Gold scale.
9. Describe basal, bolus and total daily insulin dose changes by treatment group.
10. Describe the time course of the endpoints (primary and secondary 1-7) from week 4 through the rest of the study.
11. Describe non-serious and serious adverse events by treatment group.

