#### **4.2.2 Safety and Tolerability Endpoints**

- Safety-related parameters including:
  - Reported hypoglycemic events;
  - Insulin dose (adjustments during the study);
  - Vital signs;
  - Physical exam;
  - ECG;
  - Standard safety laboratory parameters;
  - Incidence of adverse events (AEs) and serious adverse events (SAEs);
  - Subjective injection site discomfort as reported by subjects using a 100-mm VAS and other questionnaires;
  - Erythema and/or edema formation at site of injection assessed by an investigator using the modified Draize scale.

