## 10 CHANGES TO PLANNED PROTOCOL ANALYSIS

- Primary analysis endpoint updated to percent change from Induction 1 (baseline visit) to Induction 2 (visit 7, week 4) in plasma epinephrine concentration after 30 minutes of induced hypoglycemia with plasma glucose <50 mg/dL.
- Absolute change from Induction 1 (baseline visit) to Induction 2 (visit 7, week 4) in plasma epinephrine concentration after 30 minutes of induced hypoglycaemia with plasma glucose <50 mg/dL moved from primary to secondary endpoint.
- The primary analyses will also be performed by diabetes duration category (<15 yrs, ≥15 yrs) and included in the secondary analyses.
- The secondary endpoint of describing subject reported severe hypoglycemic events when glucose meter reading <36 mg/dL was updated to glucose meter reading <50mg/dL. This was a typo in the protocol.
- The Per-Protocol Population definition has been updated to include subjects who participate in the study through day 27 with no major protocol deviations because treatment compliance data was not captured for the study.

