## 12 LIST OF TABLES, FIGURES AND LISTINGS

The following table includes details of the tables, figures and listings (TFLs) for the study. Those marked with an asterisk (\*) are planned for the primary endpoint analysis and presentation of the accompanying safety analysis for that time period (See Section 8).

Table Number	Table Title	Shell Number (if repeat)
14.1.1.1*	Summary of Subject Disposition - All Subjects	
14.1.1.2*	Summary of Analysis Populations - All Randomized Subjects	
14.1.2*	Summary of Protocol Deviations - Intent-to-Treat Population	
14.1.3.1*	Summary of Demographic and Baseline Characteristics - Safety Population	
14.1.3.2*	Summary of Demographic and Baseline Characteristics - Intent-to-Treat Population	14.1.3.1
14.1.3.3*	Summary of Demographic and Baseline Characteristics - Per Protocol Population	14.1.3.1
14.1.4*	Summary of Medical History - Intent-to-Treat Population	
14.2.1.1*	Percent change from Induction 1 (Baseline visit) to Induction 2 (Visit 7, Week 4) in Plasma Epinephrine Concentration During Induced Hypoglycemia with PG <50 mg/dl Intent-to-Treat Population	
14.2.1.2*	Percent change from Induction 1 (Baseline visit) to Induction 2 (Visit 7, Week 4) in Plasma Epinephrine Concentration During Induced Hypoglycemia with PG <50 mg/dl Per Protocol Population	14.2.1.1
14.2.1.3*	Percent change from Induction 1 (Baseline visit) to Induction 2 (Visit 7, Week 4) in Plasma Epinephrine Concentration During Induced Hypoglycemia with PG <50 mg/dl, Sensitivity analysis 1* Per Protocol Population	14.2.1.1
14.2.1.4*	Percent change from Induction 1 (Baseline visit) to Induction 2 (Visit 7, Week 4) in Plasma Epinephrine Concentration During Induced Hypoglycemia with PG <50 mg/dl, Sensitivity analysis 2* Per Protocol Population	14.2.1.1
14.2.1.5*	Percent change from Induction 1 (Baseline visit) to Induction 2 (Visit 7, Week 4) in Plasma Epinephrine Concentration During Induced Hypoglycemia with PG <50 mg/dl, Sensitivity analysis 3* Per Protocol Population	14.2.1.1
14.2.2.1.1*	Absolute change from Induction 1 (Baseline visit) to Induction 2 (Visit 7, Week 4) in Plasma Epinephrine Concentration During Induced Hypoglycemia with PG <50 mg/dl Intent-to-Treat Population	14.2.1.1

Table Number	Table Title	Shell Number (if repeat)

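### Non-serious hypoglycemia is exempt from AE reporting throughout the study, and the SAP plans no output for its own endpoint of subject-reported hypoglycemic events

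*Protocol*

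**What the plan says.** **AE rule.** Protocol 10.6 makes two exceptions to AE reporting. One is that "hypoglycemia will not be considered an AE in this study unless the event meets one of the definitions of an SAE"; the reason offered is that the study induces hypoglycemia experimentally. The other is injection site reactions that need no medical intervention. Protocol 10.7 states that the AE reporting period "begins from the subject providing informed consent, through the last subject Visit".

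**Endpoint.** The Protocol lists subject-reported events as secondary objective 6 and as a safety-related endpoint (5.2 and 5.3.2). The SAP keeps both: objective 7 in 3.2.1 is "Describe subject reported hypoglycemic events", and 4.2.2 names "Reported hypoglycemic events" among the safety endpoints. There are four classes:

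- a: symptomatic, confirmed by a meter reading below 70 mg/dL
- b: symptomatic, with no reading or a reading of 70 mg/dL or more
- c: asymptomatic, with a reading below 70 mg/dL
- d: severe

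SAP objective 10 adds the time course of objectives 1 to 7 after Week 4. SAP 10 shows that the endpoint is still live: "The secondary endpoint of describing subject reported severe hypoglycemic events when glucose meter reading <36 mg/dL was updated to glucose meter reading <50mg/dL".

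**Outputs.** SAP 12 opens with "The following table includes details of the tables, figures and listings (TFLs) for the study". No title in it refers to subject-reported hypoglycemic events.

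**The concern.** The exemption is wider than its reason, and the route that should catch the exempted events is empty. The population was selected for impaired awareness and a severe episode in the past year, and Protocol 6.1 says: "The proposed indication is for the prevention of severe hypoglycemia in diabetes mellitus patients with recurrent severe hypoglycemia". Events between visits are therefore both a safety matter and the clinical counterpart of the hormone endpoint. A rule takes the non-serious ones out of the AE tables, and nothing planned puts them back.

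At stake is whether the report can compare the arms on symptomatic episodes, and on severe episodes that an investigator did not class as serious, both on treatment and after the infusion stops. SAP 9 states that there is no data and safety monitoring board, so no such body would make that comparison during the trial either.

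**Working it through.** No power or sample-size figure is involved. The check is a reading of scope and outputs, plus one coverage calculation.

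**1. Scope of the exemption against its reason.** Inductions take place at Visits 3, 7, 9 and 11 (SAP 7.2.9), which is four visits. The rule in Protocol 10.6 has no limit of time or place, and the period in 10.7 covers all outpatient time. Non-serious hypoglycemia on any other day is therefore not an AE.

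**2. The endpoint traced through the SAP.**

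| Place | Subject-reported events |
|---|---|
| 3.2.1 objective 7; 4.2.2; 10 | Named, kept, severe definition edited |
| 7.2 Derived Data | No derivation |
| 7.10.4 and 7.11 | No analysis |
| 12 | 0 tables, 0 figures, 0 listings |

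The nearest listing is 16.2.6.1, the Subject Insulin Diary. That diary holds total daily dose, bolus and basal insulin only (Protocol 9.5.2 and the Table 6 footnote).

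**3. The other exempted item.** Injection site reactions have their own analyses (SAP 7.11.6), four tables (14.3.7.2.1 to 14.3.7.2.4) and three listings (16.2.9.1 to 16.2.9.3). Hypoglycemia has no counterpart, which suggests an oversight.

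**4. What would still be shown by arm.**

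- CGM time and episode rates below 70, 60 and 50 mg/dL: four tables (14.2.2.9.1.1 to 14.2.2.9.2.2) and four figures (14.2.5.1.1 to 14.2.5.2.2), with ANOVA by treatment (SAP 7.10.4).
- Hypoglycemia that meets an SAE definition: Tables 14.3.1.1, 14.3.1.2, 14.3.1.4 and 14.3.2.2.

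**5. CGM coverage after treatment.** SAP 7.2.10.1 uses the 7 days before the Month 3 visit and the 7 days before the Month 6 visit, so 1 + 1 = 2 weeks. The length of follow-up depends on the time origin. Nominal visit weeks are used and visit windows ignored.

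| Time origin | Follow-up (weeks) | CGM share | Visit 7 to Visit 8 (weeks) |
|---|---|---|---|
| End of treatment (Protocol 7.1) | 12 + 1 + 12 + 1 = 26 | 2/26 = 7.7% | 12 |
| Randomization (Protocol 9.5) | 26 − 4 = 22 | 2/22 = 9.1% | 12 − 4 = 8 |

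On either reading, Visit 9 to Visit 10 is a further 25 − 13 = 12 weeks without study CGM.

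**6. Where the events would be recorded.** Table 6 has no row for collecting them. The apparent source is the iPRO2mylog diary with the meter. Use of the diary ends at Visit 7 (Protocol 9.5.7) and resumes at Visit 8. The supplied meter is required only during CGM collection periods (8.8). AE review, by contrast, is scheduled at every visit from Visit 2 to Visit 11 (Table 6).

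**The case against.** **Hypoglycemia is reported by arm.** A reader might infer that the outcome the drug is meant to prevent is not compared between arms at all. The documents do not support that: CGM-derived and serious hypoglycemia both have planned by-arm tables. But CGM carries no symptoms, consciousness or assistance, so it cannot yield classes a to d.

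**Severe events will be SAEs.** Many could be. Protocol 10.8 includes important medical events, and its examples include intensive treatment at home and convulsions without hospitalization. It does not name affected consciousness or outside help from hypoglycemia, however, so classification rests on investigator judgment. How many class d events would be judged non-serious cannot be known from the documents.

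**Post-treatment harm.** A reader might also infer that harm from insulin raised during the infusion could not be compared once it stops. That goes too far. SAEs are reported to the last visit, CGM is analyzed at Months 3 and 6, and Protocol 9.4.5 returns outpatient insulin to a baseline setting after discharge, although it does not say which baseline. What stands is that non-serious events would be largely unseen for most of follow-up.

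**General provisions.** Protocol 11.2.2 promises description of other endpoints, SAP 7.3.2 says that all data will be listed, and SAP 7 allows extra tables. These leave room for an output, so it would be wrong to say that one is ruled out. But none of them defines the events, the denominator or a table.

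**Expected events in this disease.** Keeping such events as a separate endpoint rather than as AEs is a legitimate choice, but it works only if the endpoint has an output.

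**Conclusion.** The concern holds in this form. The exemption in Protocol 10.6 reaches well beyond the four clamp visits that justify it, and the SAP specifies no derivation, table or listing for subject-reported hypoglycemic events. As planned, the arms would be compared on CGM measures and on serious events only. Non-serious events in classes a to c, and class d events not judged serious, have no planned output. After treatment, CGM reaches about 2 of 22 to 26 weeks (8% to 9%).

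This rests on two assumptions: visits fall at their nominal weeks, and SAP 12 is the complete output plan apart from unspecified additions. The severe cut-off differs between the Protocol (<36 mg/dL) and the SAP (<50 mg/dL), but the SAP declares the change, so it is not counted here. The point does not touch the primary epinephrine analysis. It concerns a descriptive safety endpoint and should be fixed, because a stated rule removes the events and nothing planned replaces them.

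**What to change.** 1. **Protocol 10.6:** limit the exemption to hypoglycemia during the induction procedure and its recovery, so that outpatient events (at minimum class d) are captured at the AE reviews already scheduled from Visit 2 to Visit 11.
2. **SAP 7.2, 7.11 and 12:** add a derivation, one by-arm table and one listing for classes a to d. The table should give subjects with events, number of events, and rate per subject-time actually covered, separately for Weeks 1-4 and follow-up.
3. **Data source:** state it for each period, and add a collection row to Table 6. The iPRO2mylog diary and the meter can serve only while they are in use; AE review has to serve for the rest of follow-up. Diary data cannot supply event rates for the gap between Visits 7 and 8.

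The cost is more AE entries at sites, one table and one listing. Recall between widely spaced follow-up visits will be less complete than a diary, so rates from the two sources should not be pooled. If follow-up is already over when the change is made, the Protocol change can no longer improve capture, but the SAP outputs can still be produced for the periods when the diary was in use.
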